#### A. Diagnosis of dislocation

1. **Standard of Care (control):** Order shoulder x-rays as felt necessary for standard of care of diagnosis of shoulder dislocation and reduction (portable XR versus done in radiology)

**2. Ultrasound (experiment):** No x-rays ordered. Initial evaluation with ultrasound; may also evaluate nearby areas for concern of fracture. Order x-rays after ultrasound as seen fit for other injuries of diagnostic uncertainty.

B. Shoulder reduction: Per standard of care

C. Confirmation of Reduction

- Standard of Care (control):** Order shoulder x-rays as felt necessary for standard of care of reduction confirmation.
- Ultrasound (experiment):** Use ultrasound for reduction confirmation. No x-rays ordered unless ultrasound did not adequately confirm

D. Post-reduction care (sling, follow-up, etc.): Per standard of care

	Control Group	Experimental Group
Diagnosis of Dislocation	Standard of Care (x-ray)	Ultrasound
Shoulder Reduction	Per Standard of Care	Per Standard of Care
Confirmation of Reduction	Standard of Care (x-ray)	Ultrasound

B. Study Population:

*Inclusion Criteria:*

1. Patients who are 18 years of age or older; *and*
2. Present to the VCU Emergency Department between August 1, 2020 and December 31, 2022; *and*
3. Have clinical signs of uncomplicated shoulder dislocation; *and*
4. Agree to participation in the study; *and*
5. Provides a written consent to be included in the study.

*Exclusion criteria:*

1. Patients who have a level 1 or 2 trauma activation, and/or;
2. Patients who are pregnant, incarcerated, or unable to consent, and/or;
3. Patients who have a past medical history of shoulder replacement in dislocated shoulder; and/or
4. Provider Discretion

E. Assessment of Resources

*1. Has sufficient access to the study population:*

Emergency Medicine attending and resident physicians will perform the study. They will already be in the Emergency Department and therefore will be notified of a patient meeting inclusion criteria and immediately be able to complete study following consenting process.

*2. Has sufficient time to conduct and complete the study:*

This will be a long-term project in the emergency department. Not all ED physicians will be participating in this study. The resident physicians and a select group of attending physicians will receive a curriculum and conduct the study.

*3. Has adequate qualified staff members to conduct the study:*

All members of the protocol are CITI trained, and will be trained in the data abstraction process once they have been approved by the IRB to work on the protocol. The resident, as a physician, is qualified to read and interpret medical records, and to accurately abstract data and guide students to abstract data from those charts relevant to the study. Any residents or medical students interacting with patients will be trained by the PI in the appropriate procedures for consenting a patient.

*4. Facility is adequate to conduct the study:*

The facility is adequate to conduct both the prospective data collection component as well as the retrospective chart review. The requirements are technological, including the point-of-care ultrasound machine, probes, and CCAG owned computers for data abstraction and analysis.

*5. Staff has been adequately trained on the protocol and their specific research related duties:*  
The co-investigators will be trained on the objectives of the protocol, as well as where in the chart to locate the variables to be abstracted for the study prior to formally collecting data for the study.

**D. Study Procedures**

- Image acquisition: Shoulder Dislocation
  - Usually curvilinear probe (footprint and depth)
  - Posterior view: Set probe just inferior to scapular spine
  - Follow the scapula LATERALLY; Look for the humeral head
    - If NOT Dislocated, the humeral head should be at same depth as scapula/glenoid
    - ANTERIOR dislocation will appear with head displaced away from probe relative to glenoid on the screen (in the anterior direction)
    - POSTERIOR dislocation will appear with head towards probe relative to glenoid on the screen (in the posterior direction)

Anterior Shoulder Dislocation

Same shoulder status-post reduction. Note head now aligned with scapula/glenoid

#### IV. DATA COLLECTION

Patient list and partial data will be sourced from the electronic medical record. Data abstraction will be completed in EPIC and billing.

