### Procedural Overview/Design:

1. Assess patient for enrollment. Apply inclusion and exclusion criteria (below).
2. Discuss Informed consent with patient. If patient consents, proceed to step 3.
3. Randomize patient with premade numbered envelopes stating standard of care or ultrasound protocol (description below).

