##### Study Procedure Data

Group assignment (control or experimental)  
Experience of person performing ultrasound if in experiment group  
Minimal: Minimal prior experience, sufficient training completed  
Moderate: Prior shoulder ultrasound experience  
Expert: Fellowship trained, or significant prior exposure

Type of sedation/block/analgesic given  
Intra-articular? Nerve block? Procedural sedation?

Technique of shoulder reduction performed

Number of x-rays ordered

If ultrasound group, what x-ray was ordered and why  
Portable?

Findings

Type of dislocation (anterior versus posterior)

Fractures identified  
Missed diagnoses

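### The patient list comes from the medical record with no search rule and no reconciliation to opened envelopes, so randomised patients without a charted dislocation could be left out of the length-of-stay comparison

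*Combined protocol and SAP*

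**What the plan says.** All references are to the combined protocol and SAP.

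- **Entry and allocation.** Section III (Methods) enrols on suspicion, before any study imaging. The inclusion criterion is "Have clinical signs of uncomplicated shoulder dislocation". After written consent, step 3 of the Procedural Overview reads "Randomize patient with premade numbered envelopes stating standard of care or ultrasound protocol".
- **Source of the list.** Section IV says "Patient list and partial data will be sourced from the electronic medical record", followed by "Data abstraction will be completed in EPIC and billing". No search rule is given: no diagnosis code, presenting complaint, order, consent flag or study identifier.
- **Mode of collection.** The facility item under Assessment of Resources in Section III refers to "both the prospective data collection component as well as the retrospective chart review".
- **Primary comparison.** Section II words the length-of-stay objective for patients who have a shoulder dislocation, sorted by the imaging with which they are managed.
- **Fields.** Under Study Procedure Data, Section IV lists group assignment and "Missed diagnoses". Bedside timings and a satisfaction survey follow.
- **Analysis.** Section V.B names the tests but no analysis population. Section VII mentions incomplete data for individual fields, not the loss of whole patients.

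**The concern.** In a trial randomised by paper envelope, the trial population is the set of consented patients for whom an envelope was opened. A list assembled from the record is safe only if it reproduces that set. Here nothing ensures that it does, and the objective is worded for a narrower group than the one randomised.

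The protection given by randomisation is at stake. If entry to the analysis depends on whether a dislocation was charted, it depends on something established after allocation, by x-ray in one arm and by ultrasound first in the other. The two analysed groups need not then be comparable. The count of missed diagnoses, the main safety information on replacing x-ray, would also be incomplete if missed cases were not on the list.

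**Working it through.** The plan has no figure to reproduce: Section V.A gives no sample size, effect size, standard deviation or loss rate. The check is a comparison of sections, followed by an illustration.

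**Step 1. Who is randomised.** Under Section III, patients with clinical signs who consent. Some may prove not to have a dislocation.

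**Step 2. Who is on the list.** Section IV allows at least two rules:
- a search on a consent or research flag, which keeps every randomised patient;
- a search on a charted dislocation, which loses patients without a dislocation and those whose dislocation was not recognised at the visit.

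The text does not choose between them and requires no check against envelope numbers.

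**Step 3. Who is compared.** Even with a complete list, Section II read literally restricts the comparison to patients with a dislocation and groups them by imaging used. Section V.B does not override this. Section III allows x-rays in the ultrasound arm for diagnostic uncertainty or inadequate confirmation of reduction, so grouping by imaging used need not match grouping by assignment.

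**Step 4. Whether the restriction is neutral.** True dislocation status at arrival precedes randomisation. If both arms established it without error and the search found patients equally well, restricting to dislocations would narrow the population without biasing the difference. The background cites studies with 100% sensitivity and specificity for ultrasound, which would support that. The plan itself does not rely on it: it collects missed diagnoses, admits operators with minimal prior experience, and in Section VII acknowledges possible misinterpretation. Charted status therefore can differ from true status, and differently by arm.

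**Step 5. What loss would do.** In one arm, let m be the share lost and d the mean stay of those lost minus the mean stay of those kept. Then

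mean(all) = (1 − m) × mean(kept) + m × (mean(kept) + d) = mean(kept) + m × d,

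so mean(kept) − mean(all) = −m × d. For the ultrasound-minus-control difference, the bias is −(m_U × d_U) + (m_C × d_C), which is zero when the two products are equal.

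Shift in one arm's mean, in minutes, with m and d assumed:

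| m | d = 30 | d = 120 | d = 180 |
|---|---|---|---|
| 1% | 0.3 | 1.2 | 1.8 |
| 5% | 1.5 | 6 | 9 |
| 10% | 3 | 12 | 18 |
| 15% | 4.5 | 18 | 27 |

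The sign follows d, which is unknown. Patients without a dislocation skip reduction and may leave sooner, and those with a delayed diagnosis may stay longer. The only length-of-stay figure in the documents is 30 minutes, from a study of diagnostic radiographs cited in Section I. It gives a sense of scale but is not a planned effect.

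**The case against.** The strongest reply is that the investigators probably intend to list consented patients and fill in chart fields from the record. Section IV calls the record-sourced data partial, which implies another source. The facility item names a prospective component. Group assignment can come only from the envelope, and bedside timings and survey answers are unlikely to be in billing. Written consent is an inclusion criterion, and missed diagnoses are a named field. On that reading nobody is lost.

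Much of this stands. It shows some prospective capture, and it rules out saying that the plan discards the envelopes. It does not close the gap. A field can be completed only for a patient already on the list, and nothing ties the list to the envelope sequence. Nor does it answer the wording of Section II or the missing analysis population in Section V.B.

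Two stronger readings are tempting:
- A reader might infer that the list will be built from dislocation diagnoses, so that dislocations missed by ultrasound vanish. No search rule is stated, and a dislocation missed on ultrasound but found on x-ray at the same visit would still be charted.
- A reader might infer a poorer trail in the ultrasound arm because Section IV (Cost Analysis) says the scan is not billed. Unbilled does not mean undocumented, and abstraction uses EPIC as well as billing. Section VIII.D, which makes patients responsible for the cost of an ultrasound or an x-ray, leaves the billing trail unclear in any case.

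**Conclusion.** The point holds as a gap that permits selection after randomisation; it does not show that selection will occur. It rests on four features of the text: a record-sourced list with no search rule, no reconciliation with consents and envelopes, an objective worded for dislocated patients by imaging used, and no stated analysis population.

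The size and direction of any bias cannot be derived. A reader might take 5% to 15% loss at 120 minutes, giving 6 to 18 minutes, as an expected bias against a 30-minute target. The documents do not support that: both inputs are assumed, loss is placed in one arm only, the sign is unknown, and 30 minutes is a background citation. Similar loss in both arms would narrow the population without biasing the difference. The change is still worth making, because it replaces the stated list source with one fixed at randomisation, at almost no cost.

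**What to change.** **Section IV.** Replace the sentence on the source of the list with text to this effect: the patient list is the log of consented patients and opened envelopes, entered in REDCap at randomisation; every envelope number is accounted for; the electronic record and billing serve only to complete data fields for patients on that log.

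**Section V.B.** State that the primary length-of-stay comparison includes everyone on the log in the assigned arm, whatever the final diagnosis, with an analysis of confirmed dislocations as supportive. Align the wording of the objective in Section II with this.

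**Cost.** A sentence or two in each place and a small amount of log-keeping. Section VI already provides for REDCap. The log should be kept from the first envelope, since it may not be possible to rebuild it reliably later. There is also some dilution. If a share q of those randomised have no dislocation and gain nothing from ultrasound, an effect E in dislocated patients becomes (1 − q) × E overall. With q = 10% and E = 30 minutes, both assumed, that is 0.90 × 30 = 27 minutes. The supportive analysis would show the effect in confirmed dislocations.

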##### Demographics

Age  
Gender  
Weight  
Race  
Insurance Status

##### Past Medical History

Prior shoulder dislocations

##### Study Procedure Data

Group assignment (control or experimental)  
Experience of person performing ultrasound if in experiment group  
Minimal: Minimal prior experience, sufficient training completed  
Moderate: Prior shoulder ultrasound experience  
Expert: Fellowship trained, or significant prior exposure

Type of sedation/block/analgesic given  
Intra-articular? Nerve block? Procedural sedation?

Technique of shoulder reduction performed

Number of x-rays ordered

If ultrasound group, what x-ray was ordered and why  
Portable?

Findings

Type of dislocation (anterior versus posterior)

Fractures identified  
Missed diagnoses

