## **I. BACKGROUND AND SIGNIFICANCE**

The shoulder joint is the most common joint requiring reduction by emergency physicians, accounting for almost 50% of all major joint dislocations. This presentation amounts to roughly 200,000 emergency department visits each year. The estimated incidence of shoulder dislocations in the United States is 23.9 per 100,000 person/year with male gender and young age being the two largest risk factors. The current standard of care for this presentation is to identify the dislocation on both physical exam and X-ray and then confirm the success of reduction by physical exam and X-ray following reduction. X-ray imaging does expose the patient to radiation, although minimally when as compared to other radiation-based imaging. However it is now being recommended by one study that pre and post-reduction X-rays can be omitted to help decrease the length of stay, radiation exposure and overall cost. The recommendation is that X-ray can be replaced with the application of ultrasonography. The aim of this study is to further assess the efficacy of point of care ultrasonography to diagnose and gauge the reduction success of shoulder dislocations in an emergency department setting.

With increasing availability and utilization of ultrasound, multiple studies suggest that this imaging modality can play an integral role in the diagnosis of and reduction confirmation for shoulder dislocations. Studies assessing accuracy of diagnosis deemed ultrasound to be 100% specific and 100% sensitive. A recent meta-analysis concluded that ultrasound is highly sensitive and specific for shoulder reductions, dislocations, and associated fractures. Another study identified that diagnostic radiographs increased patient length of stay by 30 minutes. The ease, efficacy, and timeliness of ultrasound has the potential to decrease the length of stay for emergency department patients. A WJEM systematic review recommended that “while the data is supportive of the use of ultrasound for the diagnosis of shoulder dislocation, further studies are needed prior to routine implementation. Future studies should compare the different techniques to determine which is most

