## II. STUDY OBJECTIVE(S); INCLUDING SPECIFIC AIMS AND/OR HYPOTHESES

The primary objective of this study is to determine if there is any difference in the length of stay between patients with shoulder dislocation who are treated with traditional x-ray imaging for diagnosis and reduction confirmation and those that are treated with POCUS for diagnosis and reduction confirmation.

*Hypothesis:* The use of POCUS for shoulder dislocation and reduction confirmation will reduce the length of stay for ED patients.

The secondary objectives of this study include evaluating patient satisfaction, providing a cost analysis, time to diagnosis, confirmation of reduction, and volume of x-ray reduction.

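### The data list has no explicit item for whether the joint was reduced or what each scan or x-ray showed, so the stated aim on reduction success cannot be answered directly

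*Combined protocol and SAP*

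**What the plan says.** Section I (Background and Significance) gives the aim as to "assess the efficacy of point of care ultrasonography to diagnose and gauge the reduction success of shoulder dislocations". Section II makes the primary objective to "determine if there is any difference in the length of stay between patients with shoulder dislocation"; its secondary objectives end with "time to diagnosis, confirmation of reduction, and volume of x-ray reduction". None of these is defined further.

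Patients enter under the Section III criterion "Have clinical signs of uncomplicated shoulder dislocation". For confirmation, the control arm is told "Order shoulder x-rays as felt necessary for standard of care of reduction confirmation". In the ultrasound arm the scan is the confirming test: "No x-rays ordered unless ultrasound did not adequately confirm".

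Section IV, Study Procedure Data, has a line reading Findings and the item "Type of dislocation (anterior versus posterior)", followed by fractures and missed diagnoses. It also lists an x-ray count, the operator's experience and, for the ultrasound group, which x-ray was requested and the reason. Confirmation of reduction appears once more in Section IV, under Timeline in ED, after the time taken to scan. Section V.B assigns paired t-tests to the secondary outcomes.

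**The concern.** The intervention replaces one confirming test with another. A reader of the results will ask how long patients stayed, and also how often the replacement test did its job. The second question needs a record of what the scan showed before and after the manoeuvre, and of whether the joint was back in place. The list has no such record, and the dislocation-type item shows no value for a patient whose shoulder proves not to be dislocated.

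A shorter stay in the ultrasound arm could then not be weighed directly against how often ultrasound confirmed the reduction. The plan itself names the risk: Section VII accepts that operators may misread scans, and Section VIII.B that an insufficient scan could delay treatment. Operator experience is collected, but there is no scan result to relate it to.

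The loss may be permanent. Section IV takes data from the electronic record and billing, and its Cost Analysis entry says the study scan will not be billed. Nothing in the documents requires the bedside reading to be written down.

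**Working it through.** No arithmetic applies beyond a count: the plan gives no sample size, event rate or power for this objective. The check sets what must be known against what is listed.

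| Needed | Listed in Section IV? |
|---|---|
| Joint reduced, yes/no | No item |
| Ultrasound reading before reduction | No explicit item |
| Ultrasound reading after reduction | No explicit item |
| X-ray reading before reduction | No explicit item |
| X-ray reading after reduction | No explicit item |
| Shoulder found not dislocated | Not shown; the type item has anterior and posterior only |
| Scan inadequate | Indirectly, through the x-ray reason in the ultrasound arm |
| Time of diagnosis and of confirmation | Probably, under Timeline in ED |
| Fractures, missed diagnoses | Yes, but not by modality or time point; missed diagnoses undefined |

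**Count.** Two modalities × two time points = 4 possible readings; 0 of 4 has its own result field.

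**The Findings line.** It may be a heading or a field. If a field, it carries no modality or time point, so it cannot separate the two tests in a patient who had both.

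**The secondary objective has two readings.**

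- *As a time.* It follows time to diagnosis in Section II, recurs in the timeline list, and is assigned a t-test, which suits a duration. On this reading it may be derivable. One doubt remains: if the timeline entry is a sub-item of scan duration, control patients have no value and the arms cannot be compared. The wording alone does not settle this.
- *As a result.* Whether reduction was achieved and confirmed has no field, and a t-test does not suit a yes/no outcome.

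Either way, a time cannot answer the Section I aim of gauging success.

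**Would result fields give accuracy?** No. Section III plans no ultrasound in the control arm. In the ultrasound arm, x-ray follows an inadequate scan, other suspected injury or diagnostic uncertainty. Patients with both tests are therefore selected for difficulty.

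**The case against.** The strongest reply is that the gap is narrower than it looks.

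- **More is collected than dislocation type.** A reader might infer that type is the only finding held. It is not: fractures, missed diagnoses, x-ray count and x-ray reason are listed too. Because post-reduction x-ray in the ultrasound arm depends on an inadequate scan, the reason item gives a workable, indirect count of scan failures. This stands. It gives no reading, however, and misses any inadequate scan that led to no x-ray.
- **The secondary objective may simply be a time.** A reader might infer that it cannot be derived at all. The documents do not support that, for the reasons given in the working. What stands against the plan is that the term is undefined.
- **The aim sits in the background section.** That section closes by naming length of stay, x-ray reduction and satisfaction as what will be evaluated, and Section II names neither accuracy nor agreement. This lowers the weight of the point. It does not remove a sentence that states the study's aim in terms the data cannot meet.
- **Section IV is a variable list, not a coded form.** The final form may hold more values, including one for no dislocation. That is possible, but the list is the only specification given.

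**Conclusion.** The concern holds in a limited form. As written, reduction success and direct scan results cannot be derived: none of the four possible readings has an explicit field, and no item records whether the joint was reduced. Inadequate scans can be counted only indirectly. Confirmation of reduction is undefined and may be derivable if it means a time.

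This rests on taking Section IV as the full set of variables. How many enrolled patients will prove not to be dislocated is not given, and the point does not depend on it.

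Two stronger inferences should be resisted. The length-of-stay comparison is not affected. Nor would better recording turn the trial into an accuracy study, because the design gives no patient both tests routinely.

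The change is worth making before enrolment, or as early as possible, since an unrecorded bedside reading may not be recoverable.

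**What to change.** 1. **Data.** In Section IV, Study Procedure Data, add one row per imaging study in both arms: modality; before or after reduction; reading (anterior, posterior, other, not dislocated/reduced, indeterminate). Enter the ultrasound reading before any x-ray is viewed. This concerns the order of recording only, not when an x-ray may be requested.
2. **Outcome.** In Section II, define the secondary outcome as the proportion of patients with reduction confirmed by the allocated modality without a second modality. Report time to confirmation separately. State the denominator, show patients found not dislocated as their own category, and say how a control patient with no post-reduction x-ray is counted, since control x-rays are discretionary.
3. **Analysis.** Compare the proportion between independent groups. Section V.B already names chi-square or Fisher's exact test for categorical variables; exempt this outcome from the paired t-test. Report the difference in proportions with a confidence interval.
4. **Reporting.** Do not present scan/x-ray agreement as accuracy. If it is shown at all, say how patients with both tests came to have them.

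If the sponsor does not want the extra fields, the alternative is to narrow the Section I aim to time and x-ray use.

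Cost: a short addition to the REDCap form, a brief outcome definition, and an estimated minute of bedside entry per scan.
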